**6 month Visits:**

The patient will have MOCA, GDS, CDR, and other neuropsych similar to screening and baseline.

**PET for amyloid.**

Most participants will who enroll in this study will have previous biomarker evidence of AD from either a brain amyloid PET scan or or CSF amyloid  $\beta$  measurement. If needed, a PiB PET scan will be performed prior to  $^{11}\text{C}$ -PBR28 imaging. We expect we will need do up to 10 PiB PET scans under this protocol.

Subjects in the MCI cohort who have a PiB-PET scan will learn their results. The following will be discussed with them:

“Amyloid” or “beta-amyloid” forms plaques in the brains of people with Alzheimer’s disease. Scientists believe that the buildup of amyloid in the brain may play a key role in the eventual development of Alzheimer’s disease-related memory loss. It is expected that about 60-70% of people with symptoms of mild cognitive impairment will have elevated brain amyloid. Research studies suggest that individuals with mild cognitive impairment who have elevated brain amyloid are more likely to have cognitive decline caused by Alzheimer’s disease. In addition individuals with mild cognitive impairment who have elevated brain amyloid are more likely to progress to Alzheimer’s dementia during their lifetime than those who do not have elevated brain amyloid.

An experienced clinician will discuss the meaning of participants amyloid scan results with them by reviewing the information above and addressing any questions or concerns that they have.

If an MCI has a negative PiB-PET scan, they will not have the  $^{11}\text{C}$ -PBR28 scans.

PiB PET scan results will not be disclosed to participants in the CN cohort They will have the  $^{11}\text{C}$ -PBR28 scans regardless of their amyloid status.

**TSPO gene polymorphism:**

We will genotype the patient with regards to rs6971 polymorphism on the TSPO gene to exclude those who are homozygous (low affinity binders). For this we will use 50 ng of genomic DNA, amplified with PCR reaction. Control plasmids encoding for high affinity binders (C/C) and low affinity binding (T/T) will be used as controls. For the heterozygote i.e. mixed affinity binders a 1:1 mixture of both will be used.

**MRI:**

A screening MRI of the brain will be obtained using a 3.0T magnet. The MRI will ensure that patients do not meet exclusion criteria by showing evidence of infection, infarction, or other focal brain lesions. Subjects with multiple lacunes will be excluded. The MRI scan will be used for PET image registration.  $^{11}\text{C}$ -PIB PET: A screening PET scan for amyloid positivity will be obtained. Only those with a positive scan in the AD groups will be enrolled for the study.

**Cognition:**

See above.

**PET Imaging of TSPO in AD**

We will compare PBR28 binding site availability in brain regions of 7 living human subjects who have AD with that in 7 age-matched healthy controls by using the ligand  $^{11}\text{C}$ -PBR28 and PET. Dose of LPS (see below) will be administered intravenously and the subject will be reimaged at 180 minutes after the injection. Considering possible failures in scans, a total of 16 patients will be studied in 2 groups, cognitive normal AND amyloid negative versus clinical criteria for mild AD and amyloid positive to reach our goal of 7 successfully scanned subject for each group. The detailed protocol may be found

09/29/12 Version 13

in our previous publication (109). We expect that 20-30% of cognitively normal participants who receive amyloid scans under this protocol will be amyloid positive. Therefore, we will enroll up to 10 participants in the cognitively normal cohort to attain the goal of 7 participants who are cognitively normal AND amyloid negative.

Primary Outcome:

The 16 enrolled subjects will have C-PBR28 using the bolus/infusion method. Measurements will be made at baseline and 180 minutes after the injection of LPS. We will measure Total Volume of Distribution (VT) for 12 brain regions defined by MRI scan, as described (111). All primary outcomes will use the parietal ROI for calculations of both baseline activation and microglial activation reserve. For our primary outcomes we will choose the microglia activation reserve index defined as MARI =  $[(VT(LPS)-VT(\text{baseline}))/ VT(\text{baseline})] \times 100$ . In the NIMH study the greatest difference in the regional PBR28 binding between AD and cognitively normal subjects was found in the parietal lobe (7). We also found the greatest microglia activation reserve index in the parietal lobe when we applied our paradigm to young healthy controls (109). Other ROIs will be used in secondary analyses.

Statistical Considerations and Sample Size:

Several comparisons of C-PBR28 VT brain level and microglia activation reserve index in the parietal lobe will be made using Student T-test to test for a difference between group means: young healthy group vs. elderly cognitively normal, as well as AD vs. elderly cognitively normal.

Although this is intended as a pilot study we have performed some basic power analyses. For the comparison of baseline activation in AD vs. aged matched cognitively normal subjects based on standard deviations derived from Kreisel (7) and our own previous studies (107,109,111), using an alpha of 0.05 and power of 0.80, our study is powered to detect an effect size of  $> 1.6$  which is not far off from the findings in the NIMH study. For the comparison of percentage post-LPS change from baseline in AD and NC groups we are powered to detect an effect size of more than 2.

Endotoxin Administration ([name] protocol.)

Endotoxin administration Subjects will receive intravenous administration of open-label endotoxin at a dose of 0.4 ng/kg body weight. This will take place at the Yale PET Center. All subjects will fast for at least 8 hours before endotoxin administration to reduce the risk of nausea, but they will be encouraged to hydrate well. They will be asked not to use aspirin, NSAIDs, COX-2 inhibitors, or acetaminophen for at least 3 days prior to each study day. Clinical Center Reference Endotoxin (CCRE) will be provided by the NIH Clinical Center and will be stored and prepared by the YNHH IDS pharmacy. CCRE is an investigational drug, and investigator [name] has obtained an Investigational New Drug (IND) for its use in humans from the Food and Drug Administration (FDA). CCRE vials will be stored at 2-8°C in a refrigerator in the locked YNHH IDS pharmacy. Preparation of CCRE will be performed by the YNHH IDS research pharmacist. As recommended by NIH, the pharmacist will dissolve the lyophilized CCRE in Sterile Water for Injection USP under a laminar flow hood on the evening before each endotoxin administration. The dissolved CCRE will be stored at 4°C until the following morning. Dissolved CCRE is stable for at least 24 hours at this temperature.

On the day of endotoxin administration, subjects will rest on a stretcher in the PET Center. An IV catheter will be placed to allow for hydration with normal saline, endotoxin infusion, and optional blood draws. In the case of bradycardia or hypotension, this catheter will be used for rapid bolus infusion of normal saline. To reduce the already low risk of adverse cardiovascular events, subjects will be hydrated with 500 mL of saline prior to endotoxin administration, and they will receive approximately 100 mL/hr thereafter for the duration of the endotoxin administration day.

After endotoxin administration, vital signs (blood pressure, heart rate and temperature) will be recorded every 15 minutes for the first two hours. If vital signs change significantly, monitoring will continue at least every 30 minutes, or more frequently as determined by the study MD, until they have returned to within 10% of the baseline values. All subjects will be connected to continuous two-lead EKG monitoring for the duration of the challenge. All subjects will be carefully monitored at all times by a research nurse and by a study physician, who will be present until 3 hours after endotoxin administration. Any subject experiencing prolonged effects of endotoxin or any other adverse event may be transferred to the Yale New Haven Hospital emergency room if appropriate.

There is no evidence that experimental endotoxin administration causes hypoxemia in humans and therefore there is no literature to support monitoring of this parameter (as opposed to parameters such as heart rate and blood pressure, which do change and which will be monitored closely). Furthermore, pulse oximetry can be unreliable when there is significant peripheral vasoconstriction, as occurs during e.g. experimental endotoxemia, sympathetic activation, and fever.

If an individual experiences bothersome symptoms after endotoxin administration and wants to stop the study, flu-like symptoms may be treated with acetaminophen (650 mg every 6 hrs- no NSAIDs will be used because of the risk of antiplatelet effects on the arterial line bleed), and anxiety may be treated with lorazepam (0.5 mg every 2 hrs for a maximum dose of 6 mg every 24 hrs). During screening each subject will be asked about medication allergies, and no medication to which a subject may be allergic will be administered. If a subject request so, the study will be stopped and these medications may be administered. In addition, if any of the following symptoms occurs, if of a severity such that it prevents normal activity, the study in that individual subject will be stopped: Chills, headache, malaise, myalgias, arthralgias, fatigue, nausea and vomiting. If a subject's body temperature exceeds 39.2°C the study will be halted and the subject will receive acetaminophen as described above. If these medications are insufficient to lower body temperature, subjects may be transferred to a higher level of care. Subjects will be discharged at the end of the study day, provided that all of the following have occurred: their blood pressure is within 10% of baseline AND their heart rate is within 20% of baseline AND their mental status is normal AND they do not feel physically or mentally unable to return home. The determination will be made by the PI and/or the study physician.

Monitoring of depressive symptoms Subjects will be rated for depressive symptoms using Geriatric Depression Scale before each endotoxin administration and at several time points afterwards. Subjects will also be rated for fatigue and pain with relevant rating scales.

#### 4. Genetic Testing N/A

##### A. Describe

- i. the types of future research to be conducted using the materials, specifying if immortalization of cell lines, whole exome or genome sequencing, genome wide association studies, or animal studies are planned

We will use 10 mL of blood to test for Ala147Thr polymorphism to identify and exclude PBR28 non-binder. Polymorphism in this gene has not clinical significance except for PBR28 testing.

- ii. the plan for the collection of material or the conditions under which material will be received

See above.

- iii. the types of information about the donor/individual contributors that will be entered into a database

The genetic polymorphism results will be entered. The results of this testing will be confidential, will not be entered into the subject's medical record, and will not be made available to the subject.

- iv. the methods to uphold confidentiality

The results of genetic testing in locked file cabinets and by separating the personal identifying information of the subjects from the genetic information.

##### B. What are the conditions or procedures for sharing of materials and/or distributing for future research projects?

No sharing is planned. Samples drawn for genetic testing will be sent to an outside lab and disposed of after testing is complete.

C. Is widespread sharing of materials planned?

No.

D. When and under what conditions will materials be stripped of all identifiers?

It will not.

E. Can donor-subjects withdraw their materials at any time, and/or withdraw the identifiers that connect them to their materials?

Yes.

F. How will requests to withdraw materials be handled (e.g., material no longer identified: that is, anonymized) or material destroyed?

Subjects will be informed that their material has been anonymized.

G. Describe the provisions for protection of participant privacy

Risks associated with genetic testing will be minimized by keeping the results of genetic testing in locked file cabinets and by separating the personal identifying information of the subjects from the genetic information.

**5. Subject Population:** Provide a detailed description of the types of human subjects who will be recruited into this study.

The subject sample of the PET study will contain both men (~50%) and women (~50%) aged 55-90. The sex ratio is expected to reflect that of other and control samples. The sample is expected to reflect the racial diversity of the state of Connecticut. Based on previous experience with similar studies in the Yale ADRU, we expect the sample to comprise mostly Caucasians, African-Americans, and Hispanics, with a relatively smaller number of Asian participants. The patients who are frail, morbidly obese, have liver disease or have multiple co-morbidities especially immunologically related.

**6. Subject classification:** Check off all classifications of subjects that will be specifically recruited for enrollment in the research project. Will subjects who may require additional safeguards or other considerations be enrolled in the study? If so, identify the population of subjects requiring special safeguards and provide a justification for their involvement.

- |  |  |  |
|--|--|--|
|  Children                        |  Healthy                           |  Fetal material, placenta, or dead fetus |
|  Non-English Speaking            |  Prisoners                         |  Economically disadvantaged persons      |
|  Cognitively Impaired |  Employees                         |  Pregnant women and/or fetuses           |
|  Yale Students                   |  Females of childbearing potential |  |

NOTE: Is this research proposal designed to enroll children who are wards of the state as potential subjects?  Yes  No (If yes, see Instructions section VII #4 for further requirements)

**7. Inclusion/Exclusion Criteria:** What are the criteria used to determine subject inclusion or exclusion?

**Inclusion Criteria:**

a- Mild AD Subjects:

1. NIA-Alzheimer's Association core clinical criteria for probable AD
2. Age between 55 and 90 (inclusive)
3. Score on the MOCA greater than or equal to 17
4. Presence of a responsible caregiver who will accompany AD subjects to all procedures.
5. Biomarker evidence of Alzheimer's disease via an amyloid PET scan or CSF amyloid  $\beta$  measurement.
6. The patient should have a capacity to consent.
7. CDR global score greater than 0.

b- Cognitively normal elderly Subjects:

1. Absence of NIA-Alzheimer's Association core clinical criteria for probable AD
2. Objective memory scores within normal range for age (do not meet MCI Subjects criterion 2)
3. Age between 55 and 90 (inclusive)
4. CDR global score of 0.0

**Exclusion Criteria:**

1. Any significant neurologic disease (other than probable AD in the AD Subjects group), such as stroke, Parkinson's disease, brain tumor, seizure disorder, multiple sclerosis, or history of significant head trauma followed by persistent neurologic deficits.
2. Any significant systemic disease including hepatic failure, heart failure, renal failure, COPD, active infection and autoimmune disease.
3. Screening/baseline MRI scan with evidence of infection, infarction, or other focal lesions. Subjects with multiple lacunes or lacunes in a critical memory structure are excluded.
4. Any significant systemic illness or unstable medical condition, including: uncontrolled or insulin-dependent diabetes mellitus, uncorrected hypothyroidism or hyperthyroidism, coagulopathy, or systemic cancer.
5. Current or regular use of over-the-counter medication that may affect the immune system (e.g., ibuprofen), including corticosteroids or immunosuppressant drugs; no use in 3 weeks prior to the PET scan
6. Investigational agents are prohibited 4 weeks prior to entry and for the duration of the study. Previous treatment with an investigational small molecule with anti-amyloid properties or passive immunization against amyloid within 1 year of study entry. Previous treatment with an active immunization against amyloid.
7. History of schizophrenia or other major psychiatric disorder (DSM IV criteria).
8. History of alcohol or substance abuse or dependence (DSM IV criteria) within the past 2 years.
9. Clinically significant abnormalities on screening laboratory tests (B12, TFTs, hematology, chemistry, urinalysis, ECG).
10. Pregnancy, as determined by screening pregnancy tests for pre-menopausal females
11. Impairment of visual or auditory acuity sufficient to interfere with study procedures.
12. Education level < 6 years.
13. Evidence of current depression as defined by a score of a score of  $\geq 5$  on the Geriatric Depression Scale.
14. Presence of pacemakers, aneurysm clips, artificial heart valves, ear implants, metal fragments or foreign objects in the eyes, skin or body. The presence of claustrophobia, precluding MRI.
15. Current or recent participation in any procedures involving radioactive agents such that the total radiation dose exposure to the subject in any given year would exceed the limits of annual and total dose

- commitment set forth in the US Code of Federal Regulations (CFR) Title 21 Section 361.1.
16. Vaccination in the last month.
  17. Drink more than 5 alcoholic drinks per week or any heavy drinking days in the last 30 days
  18. BMI > 35 or < 19
  19. Women who are pregnant or nursing, or fail to use one of the following methods of birth control unless she or partner is surgically sterile or she is postmenopausal (hormone contraceptives [oral, implant, injection, patch, or ring], contraceptive sponge, double barrier [diaphragm or condom plus spermicide], or IUD)
  20. Individuals who are classified as “low binders” for the rs6971 polymorphism (<10% of the population)
  21. Patients on antiplatelet and anticoagulant medications will be excluded.
  22. Any patient without capacity to consent will be excluded.
  23. Unstable hypertension. If blood pressure is greater than 160/100, we will contact the subject’s primary care physician to manage their blood pressure. If their blood pressure is not reduced to be consistently below 160/100 by the scanning day the subject will be excluded from the protocol.
  24. Patients with contraindications for lumbar puncture procedure can be still involved and will be excluded from the portion of the study with the lumbar puncture. These include existing intracranial space-occupying lesion with mass effect, posterior fossa mass, risk of cerebral herniation by increased CSF pressure or Arnold chiari malformation, as well as anticoagulant medication, coagulopathies and uncorrected bleeding diathesis, congenital spine abnormalities, and local skin infection at the puncture site.

**Collaborating Sites.** The Yale Memory Clinic and Yale Alzheimer’s Disease Research Unit (ADRU) will serve as the recruitment and assessment centers in this study.

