**b- How will **eligibility** be determined, and by whom?**

Eligibility to participate will be determined by the PI of this study after completion of the medical and psychiatric evaluation of the potential participant. The PI has both neurology and internal medicine training.

**c- **Risks:** Describe the reasonably foreseeable risks, including risks to subject privacy, discomforts, or inconveniences associated with subjects participating in the research.**

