**Risks associated with blood drawing and with IV and radial catheter placement.**

Blood drawing and venous catheter insertion can be associated with mild pain, bruising, infection, or clot formation. These risks are minimized by the use of proper technique. No more than a total of 150 mL of blood will be drawn during the entire study. This amount of blood loss over a period of 10 or more days should have no deleterious consequences in a non-anemic individual. On the morning of the PET scan, a radial artery catheter will be inserted by an experienced healthcare provider. The site will be anesthetized with lidocaine prior to arterial line insertion.

The arterial line will remain in place for the duration of the [11C]PBR28 scans, after which it will be removed. Arterial sampling may be associated with mild-to-moderate pain or bruising at the puncture site. In rare instances, blocking of the artery, poor healing, hematoma, inflammation, or infection at the catheter insertion site may occur. Certain individuals may feel light-headed during arterial catheter placement.

Risks of radial artery cannulation are minimized by having the procedure performed by an experienced health care provider. The health care provider would be either a physician or an advanced practice registered nurse (APRN) with experience in critical care and placement of arterial catheters, as is the practice at Yale-New Haven Hospital. For an APRN to place the arterial line at the Yale PET Center, they must meet the following criteria:

- 1.) Be currently credentialed at Yale-New Haven Hospital or similar institute and
  - 2.) Perform 3 arterial line procedures supervised by a currently privileged PET Center physician
- The 3 supervised arterial line placements will be documented and signed off by both the APRN and supervising physician. The completed document must be on file at the Yale PET Center prior to an APRN performing any arterial line catheterizations independently.

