**Pregnancy and Breast Feeding:**

Since the acceptable levels of radioactivity are lower for pregnant individuals, women will be excluded from participating in this study if they are currently pregnant or might become pregnant during the study. They will be tested for pregnancy as part of the routine laboratory tests. If the test is positive, they will not be included in the study. Before starting the study, we will ask women to avoid becoming pregnant and what precautions they plan to take. We ask women to tell us immediately if they change their minds about becoming pregnant. If the woman is currently breast-feeding, she will be excluded from the study. Women will be given one pregnancy test during the initial physical evaluation, and in addition on day of the PET scans, prior to radiotracer injection.

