**Risks of radial artery cannulation** These are minimized by having the procedure performed by an experienced healthcare provider. Pain is minimized by local anesthesia. Bleeding is prevented by local pressure applied for a minimum of 15 minutes after catheter removal. Subjects will have their hand and finger blood supply examined after arterial cannulation and again following catheter removal. Also, subjects will be asked to abstain from using aspirin and other NSAIDs for 7-10 days prior to arterial line insertion and 7-10 days following arterial line removal. Subjects will be provided a 24-hour physician [contact]) to call if they encounter pain, discoloration, numbness, tingling, coolness, hematoma, inflammation, or any other unusual symptoms in the wrist or hand, or fever, chills or drainage from the vascular puncture sites, following the procedure. In addition, if an emergency arises at the time of cannulation or scanning, 911 will be called, and the subject will be sent to the Emergency Department for evaluation and treatment. Nurses will provide the subjects an instruction sheet documenting problems to watch for and procedures to follow should such problems occur. Infection is avoided by adequate cleansing of the skin prior to intravascular line insertion.

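### Both NSAID instructions to subjects are shorter than the three-week rule in exclusion 5, and no scan-day check is stated that would catch a breach

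*Combined protocol and SAP*

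**What the plan says.** Three places in the combined protocol and SAP set an NSAID-free period before imaging.

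- **Section V.7, Exclusion Criteria, item 5.** The item begins "Current or regular use of over-the-counter medication that may affect the immune system (e.g., ibuprofen", closes that bracket, brings in corticosteroids and immunosuppressants, and ends with "no use in 3 weeks prior to the PET scan".
- **Section V.3, Endotoxin Administration.** "They will be asked not to use aspirin, NSAIDs, COX-2 inhibitors, or acetaminophen for at least 3 days prior to each study day".
- **Minimizing Risks, paragraph on radial artery cannulation.** Here "subjects will be asked to abstain from using aspirin and other NSAIDs for 7-10 days prior to arterial line insertion", with the same period again after the line is removed.

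The days from which these periods count back are set elsewhere. On the arterial line: "On the morning of the PET scan, a radial artery catheter will be inserted by an experienced healthcare provider". The section on lipopolysaccharide administration places LPS 3 hours before the second scan of that day. The imaging-visit text in Section V.3 allows the two scans to be split over two days if one long day is not tolerated.

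On when eligibility is settled: "Eligibility to participate will be determined by the PI of this study after completion of the medical and psychiatric evaluation of the potential participant". Two other conditions are tied to the day of the scan. Item 23 says of hypertension: "If their blood pressure is not reduced to be consistently below 160/100 by the scanning day the subject will be excluded from the protocol". Pregnancy is tested at the initial evaluation and "in addition on day of the PET scans, prior to radiotracer injection".

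**The concern.** The endotoxin and arterial-line texts are what subjects are asked to do. Item 5 is what they must satisfy. Neither instruction mentions 3 weeks, none of the three texts refers to the others, and nothing says which governs. A fully compliant subject can therefore be ineligible under the plan's own immune-related criterion, in a study whose primary outcome is the brain's response to an immune challenge.

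The three-week period can also run past the eligibility decision, because no interval is stated between the evaluation and the PET day. Blood pressure and pregnancy are checked on or by that day. For the last NSAID dose, no such check is stated.

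What is at stake is practical. A subject found later to have been ineligible would already have had the arterial line, the LPS and the tracer doses. The investigators would then have to decide, without a stated rule, whether to keep the scan in a comparison that aims for 7 usable subjects per group.

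**Working it through.** The plan gives no figure to reproduce here. The check sets the three windows against one another on a common clock.

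**Inputs.** Let *d* be the number of days from the last over-the-counter ibuprofen dose to the PET day. In the standard visit the line, the LPS and both scans fall on that day.

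| Rule | Place | Met when |
|---|---|---|
| Endotoxin instruction | Section V.3, Endotoxin Administration | *d* ≥ 3 |
| Arterial-line instruction | Minimizing Risks, radial artery cannulation | *d* ≥ 10 (upper limit) or *d* ≥ 7 (lower limit) |
| Exclusion 5 | Section V.7, item 5 | *d* ≥ 21 |

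**Step 1: can all three be met?** Yes. Any *d* ≥ 21 satisfies every row, so the windows nest.

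**Step 2: both instructions met, exclusion 5 breached.**

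- Upper limit: *d* = 10 to 20, which is 20 − 10 + 1 = 11 days.
- Lower limit: *d* = 7 to 20, which is 20 − 7 + 1 = 14 days.

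As shares of the 21 days *d* = 0 to 20, these are 11/21 = 52% and 14/21 = 67%. They are shares of calendar days, not probabilities of a breach. Starting the count one day later, at *d* = 11 or *d* = 8, gives 10 or 13 days and changes nothing of substance.

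**Step 3: each instruction alone against exclusion 5.** The endotoxin instruction is 21 − 3 = 18 days short. The arterial-line instruction is 21 − 10 = 11 to 21 − 7 = 14 days short. The arterial-line instruction applies to every subject, so the gap in Step 2, not the 18 days, is the one that matters for someone who follows both.

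**Step 4: would a breach be caught?** Medications are asked about at telephone screening (Section VII.4) and current medications are collected after consent (Section VIII). Item 5 can be applied at both points, but neither is described as a last-dose check on the scan day, and the interval from them to the scan is not set. In the supplied text nothing later asks about the last dose before tracer or LPS.

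**Step 5: does item 5 reach a single dose?** Its closing clause is absolute, so on its plain words it covers occasional use. The drafting is still loose. The opening speaks of current or regular use, and the closing clause comes directly after corticosteroids and immunosuppressants, so a reader could attach it to those alone. On that narrow reading an occasional ibuprofen user would not breach the item and the gap in Step 2 would be 0 days. The plain reading is the more natural one, and the gap is stated on it.

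**The case against.** The strongest reply is that nothing here conflicts. The three rules sit in different contexts: one in the endotoxin procedure, which also covers acetaminophen; one among the measures against arterial-line risk; one an eligibility rule. Different lengths for different purposes are not an error, the 3 days are a minimum, and item 5 is itself anchored to the PET scan, so the investigator can apply it up to that day. The eligibility text does not say that the decision closes after the evaluation. The consent form is a separate file and may tell subjects about the 3 weeks.

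Much of this stands. The windows are not contradictory, and what subjects are told in the consent form cannot be checked. It does not remove the point: the instructions written into the plan permit use that its own criterion forbids, and no stated step reconciles the two before LPS.

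A reader might infer more than the documents support:

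- *That item 5 is silent on occasional use.* It is not; its closing clause is absolute. The fault is loose wording.
- *That one breach costs 1/7 = 14% of a group.* This assumes that the scan is discarded and not replaced. No text requires discarding it. The imaging section of V.3 plans 16 subjects to reach 14, and Section VII.1 allows up to 10 per cohort. Part of that margin is for amyloid screening, but failure to complete is also named.
- *That MARI is biased, or that the arterial-line safeguard is weakened.* The documents give no figure for the effect of an NSAID dose taken 7-20 days earlier, and the 7-10 day rule still applies to every subject.

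**Conclusion.** The concern holds as a mismatch between instructions and criterion. A subject who follows both instructions can take over-the-counter ibuprofen on 11 of the 21 days before the scan (14 at the lower limit) and be ineligible under exclusion 5, with no stated check on the scan day.

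This rests on three assumptions: that the closing clause of item 5 means any use and reaches the over-the-counter drugs; that the visit is the standard single day; and that the consent form does not already give the 3-week rule.

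Severity is minor. No effect on the primary outcome, on power or on safety is shown, and the documents give neither the number of subjects likely to be affected nor the handling of a breach. It is still worth correcting, because the correction is cheap, changes what subjects actually do, and avoids giving LPS and tracer to someone the plan meant to keep out.

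**What to change.** 1. In Endotoxin Administration, ask subjects to take no over-the-counter NSAIDs, including aspirin and ibuprofen, for 3 weeks before each PET day. Add a cross-reference in the arterial-line paragraph. Including aspirin assumes that it belongs to the class for which item 5 gives ibuprofen as the example.
2. Keep the minimum of 3 days for acetaminophen, and leave the existing windows for prescription NSAIDs and COX-2 inhibitors unchanged. Extending 3 weeks to those would go beyond item 5, which is limited to over-the-counter products in this respect.
3. On each scan day, before tracer and LPS, record the date of the last dose, and defer the scan if the 3 weeks are not met. This should be done on both days when the scans are split.
4. Reword item 5 so that the three-week clause plainly applies to the over-the-counter drugs as well as to corticosteroids and immunosuppressants.

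The cost is one reworded instruction, one cross-reference, one clarified criterion and one field on the scan-day form. Some scan days will be rebooked, and subjects will go longer without over-the-counter NSAIDs, with acetaminophen still available until 3 days before.
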